- Describe the study, providing details regarding the study intervention (drug, device, physical procedures, manipulation of the subject or the subject's environment, etc.). Discuss justifications for placebo control, discontinuation or delay of standard therapies, and washout periods if applicable. Identify procedures, tests and interventions performed exclusively for research purposes or more frequently than standard of care. Include alternative therapies, concurrent therapies discontinued per protocol, risk benefit ratio, and use of tissue/specimens. Discuss monitoring during washout periods if applicable. Include brief description of follow-up, if any.

Research Plan. Women with breast cancer (N=190) will be randomly assigned with equal allocation to: 1) mPCST-Community or 2) mHealth-Education. Both conditions (mHealth-Ed) will involve four 50-minute individual sessions conducted over the course of 8 weeks with videoconferencing at the participant's community-based clinic or at the participant's home. Participants in mPCST-Community and mHealth-Ed will receive a smartphone to extend the intervention into their home environment. The study mobile application will provide participants in the mPCST-Community with: a mobile application that provides text and audio of intervention content tailored for low literacy, modeling video-clips, stories from other patients with pain, and other mPCST-Community materials (e.g., relaxation audio). The mPCST-Community participants will also enter daily pain, fatigue, and hassles levels and daily coping skills practice; this data will be used to send personalized messaging encouraging skills use. Innovative components of the mPCST-Community intervention include: new hybrid delivery modality (i.e., videoconferencing in community clinic, smartphone) to make such a protocol accessible to patients in medically underserved communities, adaptation for low-literacy patients, and use of personalized messaging. The therapist delivering the intervention will be at Duke University Medical Center and the participants will be at their community-based clinic. Participants may also choose to complete sessions in their home environment. mHealth-Ed participants will be given smartphones to access education session information, receive cancer education based messaging, and an education app. Participants will complete assessments at baseline, post-intervention, and at a 3- and 6-month post-intervention follow-up.

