mHealth Behavioral Cancer Pain Intervention (mPCST-Community). Participants will complete 4, 50-minute video-sessions at their community-based clinic; a therapist at Duke will deliver the session. Participants may also choose to complete their 4, 50-minute video-sessions in their home environment. Staff will be present at the community-based clinic to assist. Each site has a private room where the videoconferencing sessions will be conducted; we have used 3 of the proposed sites in our pilot studies and have successfully

set up the videoconferencing systems. mPCST-Community includes a mobile app to extend the intervention into daily life.

The therapist delivering the mHealth behavioral cancer pain intervention will be a doctoral level clinical psychologist. Once the video connection has been established, the patient and therapist will complete a session that mimics an in-person, face-to-face session. mPCST-Community sessions will be scheduled weekly with some flexibility (8 weeks to complete sessions) provided for scheduling conflicts (e.g., sickness, holidays). The content of the mHealth behavioral cancer pain intervention sessions is based on Pain Coping Skills Training (PCST) designed by [name] (Co-I). [name], along with Drs. [name], [name], and [name], has carefully designed the proposed mHealth protocol choosing particular skills shown to be efficacious in patients with cancer pain; further the protocol has been carefully designed to include content relevant to patients in medically underserved areas. PCST enhances patients ability to cope with their pain by teaching them skills to enhance their ability to manage their pain by changing their behaviors, thoughts, and feelings about pain.⁸⁹ Also, based data gathered from focus groups, the intervention protocol has been updated throughout to address fatigue as it relates to pain. We expect that the skills in this protocol will enhance patients' ability (i.e., self-efficacy): a) to use attention diversion techniques to decrease pain and distress, b) manage their pain to engage in activities that will decrease their pain, disability, and distress, and c) to use cognitive restructuring to decrease pain catastrophizing which can result in decreased pain, disability, and distress.

Selection of Subjects

- List inclusion/exclusion criteria and how subjects will be identified.

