
Data & Safety Monitoring

- Summarize safety concerns, and describe the methods to monitor research subjects and their data to ensure their safety, including who will monitor the data, and the frequency of such monitoring. If a data monitoring committee will be used, describe its operation, including stopping rules and frequency of review, and if it is independent of the sponsor (per 45 CFR 46.111(a) (6)).

This behavioral pain intervention trial carries minimal risk. All patients in the trial will continue their usual care during the course of trial, thus their doctors will provide monitoring of the patients' overall medical status. All research personnel who have direct contact with patients will be trained to observe and report any adverse event to the principal investigator. The principal investigator will report any adverse events to the institutional review board at Duke University within 48 hours. An adverse event is defined as any untoward medical occurrence during the clinical investigation that has a causal relationship to the study protocol. A serious adverse event is defined as any event which results in death, is immediately life threatening, results in persistent or significant disability/incapacity, patient hospitalization, or is serious for

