any other reason representing significant hazard. We will also appoint two data safety officers. One data safety officer will be a MD who is not associated with this study. The appointed MD officer will have experience with clinical research and trials and have a thorough understanding of adverse events. The other safety data officer will be a senior investigator who has technology expertise and will have an annual responsibility to evaluate our current mHealth system of assessment and intervention and identify any problems. All adverse events will be reported to Duke's IRB and the data safety officer in real time. All data will be stored on a secure server with multiple backups created regularly. All interactions with study participants will be under the direction of a Licensed Clinical Psychologist ([name] [PI]). Study investigators and staff for this trial will be taught to monitor for any signs that participants are experiencing high levels of physical or emotional distress that need to be addressed outside the context of this trial. If this is determined to be the case, the PI will work directly with the participant to move forward in a way that is in the best interest of the patient. No participant will be kept in the trial if they are experiencing increased extreme distress. [name] works directly with Cancer Patient Support and Care at Duke Cancer Institute as a practicing licensed clinical psychologist and as a supervisor to psychology trainees (i.e., advanced graduate students, clinical psychology interns); she is integrated into the psychosocial care program at the Cancer Center and has experience referring cancer patients who are distressed to appropriate psychosocial or psychiatric care within this large team of mental health professionals. She will use the same resources when making referrals for distress participants in this study.

Privacy, Data Storage & Confidentiality

- Complete the Privacy and Confidentiality section of the iRIS submission form.

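### Adverse events must be causally related to the protocol, serious adverse events need not be, and reporting is written only for the former, so serious events judged unrelated have no stated route to review

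*Combined protocol and SAP*

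**What the plan says.** All the relevant text is in the protocol's Data & Safety Monitoring section.

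- **Adverse event:** "any untoward medical occurrence during the clinical investigation that has a causal relationship to the study protocol".
- **Serious adverse event:** "A serious adverse event is defined as any event which results in death, is immediately life threatening", or meets one of the further seriousness criteria, which include disability and hospitalization. Causality is not mentioned.
- **Detection:** "All research personnel who have direct contact with patients will be trained to observe and report any adverse event to the principal investigator".
- **First reporting statement:** "The principal investigator will report any adverse events to the institutional review board at Duke University within 48 hours".
- **Second reporting statement:** "All adverse events will be reported to Duke's IRB and the data safety officer in real time".
- **Independent review:** two data safety officers are planned. "One data safety officer will be a MD who is not associated with this study"; the other reviews the technology. The second reporting statement refers to one officer in the singular, which I take to mean the physician.

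The section gives no separate route for serious adverse events. It names no assessor of relatedness and gives no criteria for it. It describes no log of events regardless of cause and no tabulation of events by arm.

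**The concern.** When causality is part of the definition, someone has to decide that an event is related before it counts as an adverse event. Here that decision also controls whether the event is reported, because both reporting statements use the same term. The physician officer, who is the independent check, would then see only events that someone else had already judged related.

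The judgement is hard to make in this population. Participants have stage I-IV breast cancer and pain of at least 4 on a 0-10 scale at entry (Selection of Subjects). The protocol itself foresees that practising a skill may at first provoke an adverse reaction, for example more pain or tension during muscle relaxation (Background & Significance, Social Cognitive Theory). Whether such an event comes from the intervention or the disease often cannot be settled case by case. At stake are whether serious events are independently reviewed and whether the trial can report a count of non-serious events that does not depend on opinion about cause.

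**Working it through.** No arithmetic applies, because the documents state no event rate and no share of events judged related. The check is to put each kind of event through the definitions and reporting statements as written.

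| Event | Adverse event? | Serious adverse event? | Stated route |
|---|---|---|---|
| Serious, judged related | Yes | Yes | IRB and safety officer |
| Serious, judged unrelated | No | Yes | None stated |
| Non-serious, judged related | Yes | No | IRB and safety officer |
| Non-serious, judged unrelated | No | No | None stated; not recorded |

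The second row shows the contradiction: an event can be a serious adverse event without being an adverse event.

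Two kinder readings are possible.

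1. *Serious adverse events are meant as a subset of adverse events.* The definitions then nest, but only because an unrelated death becomes neither an adverse event nor a serious one. It still has no route.
2. *The reporting statements are meant to cover serious adverse events too.* The second row is then repaired. The fourth is not, and there is still no named assessor for the fourth row or for the line between the third and fourth.

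The text does not choose between these readings, and neither closes every gap.

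The next question is what the plan captures by other means.

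- **Pain, fatigue, disability and distress** are Aim 1 outcomes. They are assessed in both arms at baseline, post-intervention, 3 months and 6 months (Design & Procedures). Study data come from patients' direct entry (Risk/Benefit Assessment), and each outcome is tested by study group (Data Analysis & Statistical Considerations, Aim 1). No causality filter applies.
- **Medical resource use from any cause** is assessed for Aim 3 and compared between arms at patient level. EQ-5D weights are also modelled by arm over time.
- **Serious events**, if collected as defined, are all-cause and could be compared by arm, although no such comparison is planned.

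Two losses remain. One is prompt independent review of serious events judged unrelated. The other is an attribution-free count of non-serious events other than the measured outcomes.

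On timing, the first statement sets 48 hours for the IRB and the second says real time for the IRB and the officer. These can coexist if 48 hours is an outer limit, but the text does not say so.

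**The case against.** The strongest reply is that this is a minimal-risk behavioral trial in which the harms that matter most are already measured. Worse pain and distress would show in the randomised Aim 1 comparison, and hospital use in Aim 3. Staff are also trained to watch for marked physical or emotional distress and involve the principal investigator, and participants' own doctors follow their medical status. None of that depends on how an adverse event is defined. All of this stands, and it limits the point. It does not replace event records: mean scores and cost data do not bring an individual death or hospitalization to the physician officer.

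A reader might infer that unmasked staff screen out harms before they are recorded. The documents do not support that. They never mention masking; only the treating therapist necessarily knows the condition. They say that contact staff observe and report, not that they judge cause. The defect is that no assessor of cause is named.

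A reader might also infer that the arms cannot be compared for safety. That is too strong, given the Aim 1 and Aim 3 comparisons and the all-cause wording of the serious-event definition. A count of related events would be distorted between arms only if attribution differed by arm, which the plan neither prevents nor establishes. With equal attribution there is under-counting alone.

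Reporting burden is a fair objection to expediting every event. It does not apply to keeping a log.

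**Conclusion.** The point holds in a limited form, and the plan should be changed. The two definitions conflict, and the reporting statements follow the narrower one. This is a stated rule that works badly if followed, not just missing detail.

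Its size is categorical: two of four event types have no stated route, and one of those, serious events judged unrelated, includes deaths and hospitalizations. How many of the 190 participants this would affect cannot be derived from the documents. The primary analysis of pain severity is untouched.

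The conclusion assumes that the reporting statements mean what the section defines an adverse event to be. If the sponsor intended them to cover all serious events, the first loss is one of wording only. The unrecorded non-serious events and the missing assessor remain.

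**What to change.** In Data & Safety Monitoring:

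1. Remove the causality condition from the adverse-event definition, so that serious adverse events become a true subset.
2. Log untoward events that come to staff attention in both arms, with seriousness and relatedness as separate fields.
3. Send all serious events to the independent physician officer, and name that officer as the reviewer of relatedness.
4. Keep expedited reporting for events that are serious or related, and tabulate the rest by arm.
5. Reconcile the 48-hour and real-time statements.

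The cost is a wording change and one log form, plus more unrelated events to log, without expedited reports for the non-serious ones.

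One limit remains. This capture is passive, and contact differs by arm: mPCST-Community participants enter daily pain, fatigue and hassles and exchange video messages with the therapist, and no equivalent is described for mHealth-Ed. Counts may therefore differ through contact alone, and the table should carry that caveat.

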Participants. Participants will be women with a diagnosis of breast cancer within the last three years. Stages I-IV will be included as recently published work suggests increased life expectancy for patients with advanced cancer⁸⁷ and significant pain is possible from both the tumor and cancer treatments during this time period.¹⁹⁻²³ Other eligibility criteria are: 1) being ≥ 18 years old, 2) having a life expectancy of ≥ 12 months, 3) report experiencing pain on at least 10 days in the last month and rate their pain in the past week as a 4 or greater on a 0-10 scale. The combination of these items assess patients level of persistent pain (in the last month) and pain severity with an accurate recall period (i.e., last week; ≥ 4). Exclusion criteria include: 1) cognitive impairment as indicated by a baseline Folstein Mini-Mental Status Examination of <25 ⁸⁸ and the Rapid Estimate of Adult Literacy in Medicine, Revised (REALM-R) or through medical chart review indicated by a baseline Folstein Mini-Mental Status of Examination <25 2) brain metastases, 3) presence of a severe psychiatric condition or a psychiatric condition (e.g., suicidal intent) that would contraindicate safe participation in the study as indicated by the medical chart, treating oncologist, or medical/study staff interactions, or 4) current or past (<6 months) engagement in PCST for cancer.

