Recruitment. Participants will be recruited from cancer clinics that are part of the Duke Cancer Network (DCN). Each clinic is in a medically underserved area and sites are in mostly rural or highly urban areas of North Carolina, South Carolina, Georgia, and Virginia and has provided a detailed letter of support. These clinics provide oncology care to patients who otherwise would have very limited access to subspecialty cancer care. We will recruit from 8 sites (see Table 2 for site, county consensus, the medically underserved index, primary care physician to patient ratio, annual number of breast cancer patients, and projected annual and total recruitment). Each clinic has staff designated to assist with trial recruitment (see letters of support from site oncologists). During study start-up, the study team will travel to each site to train staff members in procedures. Training may also take place over a videoconferencing platform. Short videos along with written information on study purpose and procedures will be produced and available to clinic staff at each site. Study staff will visit each site at least quarterly and up to twice quarterly. Our team consists of several experienced clinical trials investigators with extensive histories of successful recruitment (Drs. [name], [name], [name]). Drs. [name] (PI) and [name] (Co-I) have successfully recruited breast cancer patients to behavioral trials in the DCN clinics. The study team will closely track participant recruitment during the first year of recruitment. If recruitment is not met at 90% overall for Year 1, three of our sites (i.e., Gwinnett, Lexington, Spartanburg) have indicated that they will work with our team to increase recruitment (see letters of support; 40 additional patients annually).

We will use electronic medical records (EMR), tumor registry information, and clinic staff to identify potential patients. The clinical research coordinator will send an email to the treating oncologist to alert them of potential participants. Participating oncologists have agreed to alert the study team if they estimate a potential participant has less than 1-year to live or there is known psychotic disorder, suicidal

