The PI has completed Duke University Health System Institutional Review Board's online training course: Protecting Research Subjects, as well as human research subjects' protection training and certification through the Collaborative Institutional Training Initiative (CITI) program, both of which address confidentiality. All other individuals involved in this study will be required to complete these courses and ongoing training. The PI, mentor/co-mentor, and collaborators have conducted research in the proposed area and have not encountered participants who experience significant psychological distress as a result of study procedures. In fact, participation in the proposed interventions, particularly PCST-Community, is associated with few negative side effects and potentially multiple benefits to physical health, mood, and quality of life. The proposed significance of study findings outweighs the limited risk.

4. Recruitment and Informed Consent. All recruitment procedures will comply with HIPAA guidelines. The recruitment procedure will be as follows: Potential participants will be identified through electronic medical record review or their medical team. Once a potential participant has been identified, their primary oncologist will be contacted for permission to attempt to recruit the participant for this study. If the oncologist agrees, potential participants will be told about the study by a member of the medical staff and asked if they would be willing to talk with a member of the study team. Potential participants will also be sent a letter through postal mail letting them know that someone will call about the study or meet them at their clinic visit or give them a number to call to completely opt out of any further study activities. Once a potential subject agrees, a member of the study team in the cancer clinic will approach them in person or over the telephone. At this time, the member of the study team will describe the study in detail, provide the patient with consent forms, and offer to answer any questions about the study. Once a patient has consented, they will complete the first study assessment at that time or at a time in the future convenient for them.

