Aim 3: To evaluate cost, cost-effectiveness and practicality of mPCST-Community. **Analyses.** We will use patient-level data to test for differences between mPCST-Community and the Health-Edu conditions on medical resource use, medical costs and productivity costs. We will use generalized linear models specified using negative binomial error distributions and log links for resource use and gamma error distributions and log links for costs. We will apply mixed-effects linear regression models to test for interactions between study interventions and time on EQ-5D-derived preference weights across the 6-month follow-up period. Baseline resource use and EQ-5D weights will be included as covariates in regression models. For each patient will compute quality-adjusted life-years (QALY) using the trapezoidal rule applied to EQ-5D weights at baseline, post-intervention, 3 months and 6 months. Because the mHealth-Ed control was designed to control for patient contact time and does not represent standard care, accounting for the costs of providing this condition and patient time spent participating would inappropriately offset the costs associated with the mPCST-Community intervention. Therefore, we will modify our calculation of the numerator of incremental cost-effectiveness ratio (ICER) in which we will calculate the difference in mean medical costs and productivity costs between the mPCST-Community and mHealth-Ed control groups then add direct costs of resources required to provide mPCST-Community as well as participant time costs. To compute the difference in QALYs, we will subtract mean QALYs in the mHealth-Ed condition from mean QALYs in the mPCST-Community condition. Then, we will divide the estimated difference in mean costs by the difference in mean QALYs and generate a 95% confidence interval constructed using nonparametric bootstrapping. We then will calculate net health benefits (QALY* λ – Cost, where λ represents maximum willingness to pay per QALY) for each patient, and apply linear regression analysis to evaluate whether intervention and patient baseline characteristics are associated with improved cost-effectiveness. In sensitivity analyses, we will evaluate the impact of: (1) applying various durations of sustained benefit beyond the 6-month follow-up period; (2) excluding productivity gains/costs; and (3) assuming patients could participate in videoconferencing at home. To evaluate practicality and sustainability of PCST-Community, we will assess accrual, participant retention, and intervention protocol adherence.

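### The distress rule takes women out of the trial rather than out of sessions, so their later outcomes are lost; the bias is probably small and one added sentence would reduce it

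*Combined protocol and SAP*

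**What the plan says.** Data & Safety Monitoring has staff "taught to monitor for any signs that participants are experiencing high levels of physical or emotional distress". When such distress needs attention outside the trial, the principal investigator works with the woman to "move forward in a way that is in the best interest of the patient". The next sentence is categorical: "No participant will be kept in the trial if they are experiencing increased extreme distress".

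The surrounding text matters in four ways.

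- **Outcomes.** Aim 1 lists psychological distress among its outcomes, with pain severity primary. Background & Significance reports that pain and distress are related.
- **Follow-up.** The Research Plan sets assessments at baseline, post-intervention, and 3 and 6 months later. It does not say whether a removed woman is still assessed. The statistical section has no intention-to-treat statement and no rule for withdrawn women.
- **Retention and adherence.** For Aim 3, "we will assess accrual, participant retention, and intervention protocol adherence", so the plan counts staying in the study and following the intervention as different things.
- **Missing data.** Statistical Power & Analyses plans a repeated-measures mixed model. Aim 1 describes missingness by group, with an eye to differential drop-out, and adds a propensity-score sensitivity analysis.

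**The concern.** Stopping an intervention and stopping data collection are separate decisions, and the removal sentence makes both at once. The women affected are selected on a variable the trial is measuring. Their later scores would probably be among the worst in their arm on distress and, through the correlation, worse than average on pain. The missing outcomes would be created by the protocol, not by refusal.

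The planned analyses work from recorded data. The trigger is signs noticed by staff, possibly between the four scheduled assessments. If removal depends on distress that no visit captured, and its rate or mechanism differs between arms, neither the mixed model nor propensity scoring fully corrects the comparison. At stake are some bias in the Aim 1 effects, larger on distress than on pain, and the loss of follow-up on the women who fared worst.

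**Working it through.** **1. The plan's own figure.** Aim 1 gives 72 per group (90 less 20%: 90 × 0.80 = 72) and 80% power for an effect of about 0.48. Alpha is not stated; I assume 0.05 two-sided. A two-sample t test with 72 per group and d = 0.48 has power 0.816, so the figure reproduces. With the plan's example SD of 2.0, the standard error of the pain difference is 2.0 × √(2/72) = 0.333 points.

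**2. Assumptions.** The documents give no removal rate, so 1%, 2% and 5% of controls are illustrations. Further assumptions are a true effect of 0.48 SD on both outcomes, a distress–pain correlation of 0.5, the same removal threshold in both arms, and a trigger identical to the distress outcome with no covariate adjustment. The last makes this a worst case within the common-threshold setting.

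**3. Common threshold.** Control distress is N(0,1), mPCST-Community N(−0.48,1), and women above the cut c are removed. The mean of those retained is μ − φ(c−μ)/Φ(c−μ). At 1%, c = 2.326: control −0.0269, mPCST −0.4878, difference 0.461, loss 0.0191 SD. The pain loss is 0.5 × 0.0191 = 0.0096 SD, and × 2.0 gives 0.019 points.

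| Controls removed | mPCST removed | Distress effect | Pain effect | Pain loss, points | Share of SE |
|---|---|---|---|---|---|
| 1% (about 1 of 95) | 0.25% | 0.461 (−4%) | 0.470 | 0.019 | 6% |
| 2% | 0.56% | 0.447 (−7%) | 0.463 | 0.033 | 10% |
| 5% | 1.68% | 0.414 (−14%) | 0.447 | 0.066 | 20% |

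With correlations from 0.3 to 0.7, the pain loss is 0.011–0.027 points at 1% and 0.04–0.09 at 5%.

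**4. Power.** Cutting the upper tail also shrinks the SD of retained women. For pain the pooled SD becomes 0.995, 0.991 and 0.982 of its original value. The standardised effects are 0.470/0.995, 0.463/0.991 and 0.447/0.982, and power with 72 per group is 0.805, 0.796 and 0.774, against 0.816. Holding the SD at 1 would give 0.801, 0.789 and 0.759, which overstates the loss.

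**5. Baseline adjustment.** The planned model includes the baseline score. In a simulation of 4 million with baseline correlations of 0.5 and trigger–outcome correlations of 0.6 to 1.0, the adjusted distress effect is 0.473–0.464 at 1% and 0.456–0.428 at 5%. These are losses of 1.5–3.3% and 5–11%.

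**6. Without a common threshold.** The Research Plan has mPCST-Community women enter pain, fatigue and hassles daily and describes no equivalent for mHealth-Ed. Suppose there is no true effect, and the worst 2% of mPCST and 1% of control women are removed. The retained means are −0.0494 and −0.0269, a spurious difference of 0.022 SD on distress in favour of the intervention.

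More generally, if removed women are worse than retained women by the same gap in both arms, bias = (control share − mPCST share) × gap. A 5-point imbalance with an assumed gap of 1 to 3 pain points gives 0.05–0.15 points. The upper end exceeds the 0.066 in the table, so the table does not bound the problem once thresholds differ.

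**The case against.** **Size.** At 1%, about one control woman goes and the pain effect moves by 6% of a standard error. No decision about the trial would turn on that. This stands, and it limits the point to an improvement worth considering.

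**Few removals.** Eligibility already excludes "presence of a severe psychiatric condition or a psychiatric condition (e.g., suicidal intent) that would contraindicate safe participation in the study". Under Recruitment, "Participating oncologists have agreed to alert the study team" to such conditions. The risk section says the team and collaborators "have not encountered participants who experience significant psychological distress as a result of study procedures", and the monitoring section opens "This behavioral pain intervention trial carries minimal risk". These make low numbers likely, but none gives a rate; they fit zero as well as 1%. The last two also concern study-related risk, and breast cancer can cause distress by itself.

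**Reading.** The sentence sits in a safety section and may only promise that nobody is held in against her interest. That is a fair reading of intent, and the best-interest wording allows individual handling. It does not override a categorical sentence about being kept in the trial, or say that assessments continue.

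**Existing handling.** The mixed model uses scores recorded before removal, and drop-out is examined by arm. This helps in part. In a simulation with removal after a recorded post-intervention visit, using that score and baseline corrected about 34–53% of the loss; the share depends on the assumed correlations.

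**Unseen text.** Consent content is in a separate form and may provide for continued follow-up. This stands as a condition on the fix.

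**Stronger readings.** A reader might infer that the rule threatens the primary result, or could manufacture a positive finding. The documents do not support that: no removal rate or difference in detection is stated, equal removal of equally affected women gives zero bias when there is no true effect, and the illustrated biases are well below the 0.48 SD design effect. Nor do they support the opposite inference, that the bias must be conservative. That needs a common threshold, which the plan does not state.

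**Conclusion.** The point holds as a minor design improvement. The sentence as written ends outcome assessment together with participation, for women selected on an Aim 1 outcome, and no supplied text separates the two. The planned analyses correct this only in part.

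The likely effect is small and greater on distress than on pain. Even at the high case of 5%, the common-threshold pain loss is a fifth of a standard error. The direction is towards understating a real benefit if the threshold is common, and uncertain if staff notice distress more readily in one arm. Every size here rests on assumed removal rates and correlations. Confidence is medium, because the rate is unknown and the consent form was not available.

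**What to change.** Leave the clinical decision unchanged. After the removal sentence in Data & Safety Monitoring, add:

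> A woman who stops sessions for distress stays in the post-intervention, 3- and 6-month assessments unless she declines or the PI judges further contact unsafe, is analysed as randomised, and has the date and reason recorded by arm.

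If the consent form already provides for this, the protocol need only be aligned with it. Recording the reason by arm would show whether removals differ between groups. A delta-adjusted sensitivity analysis for women who decline is optional, and worth doing only if there are more than one or two.

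The cost is one sentence, with no change to sample size or model. The downside is that a few questionnaires are offered to distressed women. Some will decline and others may be judged unsafe to contact, so some outcomes will still be missing.
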